No imputation of missing data will be performed.

The response to increasing i.a. doses of C21 will be summarised using descriptive statistics with percent change from baseline and presented by dose.

The dose response curve of C21 will be presented using a mixed model. The natural logarithm of the maximum FBF value for each dose level and each subject will be used as the dependent variable in the model. Kenward-Roger's approximation for degrees of freedom will be used. The least square means (LSMeans) estimates for the doses will be presented in a plot. In addition, the pairwise LSMeans differences between the doses will be tabulated.

Study reporting

After completion of the study, an International Council for Harmonisation (ICH) E3 compliant Clinical Study Report (CSR) will be prepared.

2	TABLE OF CONTENTS	
1	STUDY SYNOPSIS	2
2	TABLE OF CONTENTS	6
3	LIST OF ABBREVIATIONS AND DEFINITIONS OF TERMS	11
4	IMPORTANT MEDICAL PROCEDURES TO BE FOLLOWED BY THE INVESTIGATOR	14
4.1	Medical emergencies contacts	14
5	INVESTIGATOR AND STUDY ADMINISTRATIVE STRUCTURE	15
6	INTRODUCTION	17
6.1	Background	17
6.2	Non-clinical data	17
6.3	Clinical experience	
6.4	Venous occlusion plethysmography	20
6.5	Study rationale	20
6.6	Risk/benefit assessment	20
6.	6.1 Risks associated with arterial cannulation	21
6.	6.2 Risks related to local tolerance	21
6.	6.3 Risk assessment with regards to the COVID-19 pandemic	22
6.	6.4 Risk-benefit conclusion	24
7	STUDY OBJECTIVES AND ENDPOINTS	25
7.1	Primary objective	25
7.	1.1 Primary endpoint	25
7.2	Secondary objectives	25
7.	2.1 Secondary endpoints	25
8	STUDY DESIGN	26
8.1	Overall study design and schedule of events	
8.2	Rationale for study design	
8.	2.1 Selection of starting dose and rationale for planned dose escalation	29
9	STUDY POPULATION	
9.1	Recruitment	30
9.2	Screening and enrolment log	30
9.3	Number of subjects	
9.4	Inclusion criteria	30
9.5	Exclusion criteria	
9.6	Restrictions during the study	

9.6.1	General restrictions	
9.6.2	Prior and concomitant therapy	
9.7	Screen failures	33
9.8	Subject withdrawal	34
9.8.1	General withdrawal criteria	
9.8.2	Withdrawal in case of extravascular cannulation	
9.8.3	Procedures for discontinuation of a subject from the study	
9.8.4	Subject replacement	
9.9	Randomisation and blinding	34
10	ΓREATMENTS	35
10.1	Identity of investigational medicinal products	35
10.1.	1 Test product	
10.1.	2 Comparator product	
10.2	Manufacturing, packaging, and labelling and release	35
10.3	Conditions for storage	35

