The subject will receive ascending doses of C21 (3, 10, 30, 100 and 200 μ g/min) through local i.a. infusions for 5 min/dose with an infusion rate of 1 mL/min or 2 mL/min for the 200 μ g/min dose. The start -and stop times of the infusions will be recorded. Measurements of FBF will be performed in both arms simultaneously during the last 2 min of each infusion. The C21 doses will be separated by a wash-out period of at least 15 min. At the end of each wash-out period FBF will be measured and a baseline value for the next dose be recorded.

For each FBF measurement, an inflation pressure of 60 mmHg will be used for intervals of approximately 7 sec followed by approximately 8 sec of deflation. This cycle will be repeated approximately 8 times during the last 2 min of each infusion. The wrist cuff will be inflated to supra-systolic pressures within 30 sec before each measurement to exclude the hand circulation. Changes in forearm volume will be measured using strain-gauges placed around the widest part of the forearms. A measure of blood flow to that part of the forearm enclosed by the two cuffs is provided, expressed as mL per 100 mL of forearm volume per minute. Actual forearm volume can be estimated by calculation, assuming the forearm is a simple truncated cone, or by simple water displacement.

When the last C21 dose has been administered, the infusion will be discontinued and there will be a resting period of 20 min. At the end of this resting period, FBF will be measured and a baseline value for the first sodium nitroprusside dose will be recorded.

Infusions of sodium nitroprusside solution (Nipruss[®]) will be performed as a positive control, using the same methodology as described above. Ascending doses of 0.8, 1.6, and 3.2 μ g/min will be administered.

After removal of the arterial catheter a compression bandage will be applied to prevent bleeding.

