17 STATISTICAL METHODS AND DETERMINATION OF SAMPLE SIZE

The principal features of the statistical analysis to be performed are described in this section. A more technical and detailed elaboration of the principal features will be presented in a separate *Statistical Analysis Plan*, which will be signed and approved prior to database lock.

Analyses of the primary and secondary endpoints will be performed by CTC.

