17.5.2 Dose-response

The dose response curve of C21 will be presented using a mixed model. The natural logarithm of the maximum FBF value for each dose level and each subject will be used as the dependent variable in the model. Dose will be used as a class variable and subject as a random variable. Kenward-Roger's approximation for degrees of freedom will be used. The least square means (LSMeans) estimates for the doses will be presented in a plot. In addition, the pairwise LSMeans differences between the doses will be tabulated.

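### The dose-response model uses the log of the maximum FBF per dose, which overstates flow by an amount set by reading scatter, reading count and artefacts; the mean of acceptable readings is the safer summary

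*Combined protocol and SAP*

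**What the plan says.** Section 17.5.2 sets the outcome of the mixed model as "The natural logarithm of the maximum FBF value for each dose level and each subject", and the synopsis repeats this. The model terms are given in one sentence: "Dose will be used as a class variable and subject as a random variable". The curve itself is the set of dose estimates: "The least square means (LSMeans) estimates for the doses will be presented in a plot". Pairwise differences between doses are to be tabulated.

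The measurements behind the outcome are in section 11.2.1. There is one window per infusion: "Measurements of FBF will be performed in both arms simultaneously during the last 2 min of each infusion". Within it the cuff is inflated for "intervals of approximately 7 sec followed by approximately 8 sec of deflation", and "This cycle will be repeated approximately 8 times during the last 2 min of each infusion".

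The documents do not say whether the maximum is taken over single readings or over some average. They give no reason for choosing it, no minimum number of valid readings and no FBF-specific artefact rule. Section 17 does look ahead: "A more technical and detailed elaboration of the principal features will be presented in a separate" statistical analysis plan, to be approved before database lock.

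**The concern.** The largest of several noisy readings of a steady flow lies above that flow. How far above depends on how scattered the readings are and how many there are, and neither is a property of the drug. The dose-response curve is a named secondary endpoint, and section 6.5 says the study data are meant to guide the design of later studies. A curve whose height partly reflects measurement scatter is a weaker guide than one built on an average of the same readings. With 5 subjects, any avoidable noise in the dose comparisons also matters.

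**Working it through.** **Inputs from the documents.** One 2-minute window per infusion; 7 s inflation plus 8 s deflation per cycle; 5 C21 doses; 5 subjects. Check of the stated count: 120 / (7 + 8) = 8.0 cycles, which agrees with section 11.2.1.

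**Assumptions.** The documents give no SDs. I take a reading log-SD s (scatter of single log-readings within a window) of 0.10 or 0.20, a subject-by-dose log-SD t of 0.05, 0.10 or 0.20, and normal log-readings, either independent or AR(1) with correlation 0.7. The log is monotone, so the log of the maximum is the maximum of the log-readings.

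**1. Level shift.** For independent readings, normal order statistics give E[max] = 1.163, 1.267, 1.352 and 1.424 SDs for 5, 6, 7 and 8 readings. For 8 readings at AR(1) 0.7, simulation gives 1.052. The shift is exp(E[max] × s) − 1:
- s = 0.10: exp(0.1424) − 1 = 15.3% independent; exp(0.1052) − 1 = 11.1% at AR(1) 0.7.
- s = 0.20: exp(0.2848) − 1 = 32.9% independent; exp(0.2104) − 1 = 23.4% at AR(1) 0.7.
- The log of the mean is off by at most about +0.5% (s = 0.10) or +1.8% (s = 0.20).

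**2. Dependence on count.** Independent readings, 5 usable instead of 8: exp((1.163 − 1.424) × 0.10) − 1 = −2.6%; at s = 0.20, −5.1%. With 7 or 6 usable readings at s = 0.10 the change is −0.7% or −1.6%.

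**3. Dependence on scatter.** With the same true flow but s = 0.10 at one dose and 0.12 at another, the spurious difference is exp(1.424 × 0.02) − 1 = +2.9% (independent) or exp(1.052 × 0.02) − 1 = +2.1% (AR(1) 0.7). With equal s and equal count the shift is the same constant at every dose and drops out of the differences.

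**4. One missed artefact** (independent, s = 0.10, simulated). One reading of 8 that is 20% too high moves the maximum +7.0% and the mean +2.5%. One that is 50% too high moves them +30% and +6.3%.

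**5. Precision of dose differences.** Var[max] = 0.3729 against Var[mean] = 0.125 (independent), ratio 2.98; 0.6256 against 0.4783 (AR(1) 0.7), ratio 1.31. The residual variance ratio is R = (t² + s²·Var[max]) / (t² + s²·Var[mean]), and 5 subjects then act like 5/R. At s = 0.10:
- t = 0.05, independent: (0.0025 + 0.003729) / (0.0025 + 0.00125) = 1.66, so 5 act like 3.0; AR(1) 0.7: 1.20, like 4.2.
- t = 0.10: 1.22 (4.1); AR(1) 0.7: 1.10 (4.5).
- t = 0.20: 1.06 (4.7); AR(1) 0.7: 1.03 (4.8).

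At s = 0.20 the ratios for the same three values of t are 2.32, 1.66 and 1.22 (independent) and 1.27, 1.20 and 1.10 (AR(1) 0.7).

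The upper 95% limit of a dose ratio above its estimate, with complete data and (5 − 1)(5 − 1) = 16 df, is exp(2.120 × √(2(t² + v)/5)) − 1, where v is s² times the relevant variance. For s = t = 0.10, independent: maximum, exp(2.120 × √(2 × 0.013729/5)) − 1 = 17.0%; mean, exp(2.120 × √(2 × 0.01125/5)) − 1 = 15.3%.

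**6. Precision of the plotted LSMeans.** These also carry between-subject variance b². The ratio is (b² + t² + s²·Var[max]) / (b² + t² + s²·Var[mean]). With b assumed at 0.20 to 0.30, s = 0.10 and t from 0.05 to 0.20, it is 1.02 to 1.06 (independent) or 1.01 to 1.03 (AR(1) 0.7). At s = 0.20, b = 0.20, t = 0.05, independent, it is (0.04 + 0.0025 + 0.014916) / (0.04 + 0.0025 + 0.005) = 1.21.

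**The case against.** Four points deserve weight.

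First, no section says that the curve should estimate average flow over the window, so the upward shift exists only relative to a target that the reader supplies. That is fair as far as it goes. But a maximum chosen for its own sake still varies with scatter, usable count and artefacts, and the plan gives no reason for wanting it.

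Second, the text does not state what the maximum is taken over, and the separate SAP may define it. This stands as a limit on every figure above. However, the maximum is already fixed in both 17.5.2 and the synopsis, and with one window per dose the single readings are the natural set.

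Third, a reader might infer that the dose comparisons are biased, that the maximum is always noisier, or that the primary endpoint is affected. The documents do not support any of these. With equal scatter and count the shift cancels in the differences. The variance ratio falls to about 1.08 at AR(1) 0.9, and for uniformly distributed readings the two summaries are about equally noisy (SD 0.344 against 0.353 reading-SDs). Section 17.5.1 does not specify the maximum for the primary endpoint.

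Fourth, the mean has its own cost if flow is still rising in the window. For an assumed linear 20% rise against a flat dose, the mean understates the end-of-infusion contrast by 1 − 1.1/1.2 = 8.3%. The maximum understates it by about 4% to 7% in simulation, depending on scatter. This stands, and is the reason to keep the maximum as a sensitivity analysis.

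**Conclusion.** The point holds as a worthwhile improvement to a secondary, descriptive analysis. If the maximum is over the roughly 8 single readings, the plotted curve sits too high as an estimate of flow: by 11% to 15% at an assumed reading log-SD of 0.10, or 23% to 33% at 0.20. It is also exposed to changes in usable count and to single artefacts. The loss of precision in dose differences runs from negligible (5 subjects acting like 4.8) to material (like 3.0) at reading log-SD 0.10, and it is larger at 0.20 when subject-by-dose variation is small. The precision of the plotted LSMeans changes by only about 1% to 6% in variance at reading log-SD 0.10. All these sizes rest on assumed SDs and correlation and on roughly normal log-readings. No test or success rule depends on the curve, so the harm is confined to the estimates and the plot.

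**What to change.** In 17.5.2 and the synopsis, make the dependent variable the natural log of the mean of the technically acceptable FBF readings in the last 2 minutes of each infusion. In the SAP, before database lock, set the acceptability criteria and a minimum number of readings, and list the number used per dose and subject. Keep the log of the maximum as a sensitivity analysis, and state what that maximum is taken over.

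The cost is wording in the protocol and SAP, with no extra data. The drawback is that a brief peak, or flow still rising within the window, is averaged. The change does not settle how the non-infused arm enters the analysis, and it does not require any edit to 17.5.1 or 17.5.3.

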17.5.3 Effect of sodium nitroprusside on forearm blood flow

The response to increasing i.a. doses of sodium nitroprusside will be summarised using descriptive statistics with percent change from baseline and presented by dose.

17.6 Analysis of safety endpoints

17.6.1 Adverse events

An overview of all AEs, including SAEs, intensity, relationship to IMP/study procedures, and deaths will be presented by treatment group. Incidence of AEs and SAEs will be summarised by SOC and PT.

All AE data will be listed by subject and include the verbatim term entered by the Investigator.

17.6.2 Vital signs

Vital signs (systolic/diastolic blood pressure and pulse) will be summarised using descriptive statistics. Data will be presented with absolute change from baseline.

Individual data will be listed by subject.

17.6.3 12-lead ECG

All ECGs will be categorised as *normal, abnormal, not clinically significant*, or *abnormal, clinically significant* (as judged by the Investigator) and summarised using descriptive statistics.

Individual data will be listed by subject.

17.6.4 Safety laboratory analyses

Safety laboratory data will be summarised using descriptive statistics with absolute change from baseline. Abnormal, clinically significant values will be summarised separately, if considered appropriate.

Individual data will be listed by subject.

